### 8.1.2. Wearable Physiological Monitor

The BioModule™ BH3-M2 sensor is a wearable physiological monitoring device intended for monitoring adults in hospitals and alternate care settings. When combined with the BioModule Holder and snap ECG electrodes, it becomes the BioPatch™ wireless device. It continuously collects a patient's physiologic data including ECG, HR, RR, body orientation, and activity and transmits data to the Vital Sync™ VPMP every [REDACTED]. The BioModule™ sensor provides a [REDACTED], single-lead ECG that records either automatically or on demand when a patient's heart or respiration rate crosses clinician-assigned thresholds.

The BioModule™ sensor is a Class II device and 510(k) cleared by the FDA.

[figure not shown]
BioModule™

This document is electronically controlled. Printed copies are considered uncontrolled.

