## 8.4. Product Use

The Vital Sync™ IM & VPMP will be used to allow clinicians to remotely view patient information collected from the BioModule and enable clinicians to be notified of clinical distress via color coded alarms and audible alerts. The BioModule will be attached to each subject and placed on the lower section of the sternum via two electrodes.

User guides and instructions for use of the Vital Sync™ IM & VPMP and BioModule™ will be provided to the study team prior to or at the Site Initiation Visit.

This document is electronically controlled. Printed copies are considered uncontrolled.

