### 10.1. Monitoring Group Assignment

#### Telemetry Monitoring (TM) Group, Control

The TM group will serve as the control group and will be monitored via the site's standard of care telemetry practice/protocol. Subjects will continue to be enrolled in the study if subjects are transferred to medical-surgical unit after initial period of TM. Subjects will be tracked daily to confirm continuing eligibility for the study. Temporary alternate monitoring modalities will be allowed per the discretion of the Investigator. If subject no longer meets eligibility criteria, the subject should be withdrawn and study completion date will be the date the subject became ineligible not the date the study team discovered the ineligibility.

If a subject is transferred to another hospital unit or telemetry is discontinued, subject will continue to be enrolled in the study.

If subject is transferred to ICU, there will be an exception to the requirement of tracking daily continuing eligibility. It is expected for additional care and monitoring to be administered during the ICU stay and AHA indication to change. Once subject is transferred from the ICU back to a lower acuity unit, eligibility criteria will be reassessed and documented. If subject no longer meets eligibility criteria upon return to

This document is electronically controlled. Printed copies are considered uncontrolled.

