### 10.2.2. Inpatient Data Collection

Data collected during the course of the hospital stay will be limited to daily reviews of the subject status to assess continuing eligibility and to assess for AEs/SAEs, protocol deviations, and device deficiencies as applicable per Section 12.

The following procedures and assessments will be performed **during both phases of the study** on inpatient days and the results will be recorded on the subject eCRFs.

- Complete inpatient tracking form to confirm continuing eligibility for the study
- Check and record daily AEs/SAEs and protocol deviations
- Verify data and enter into eCRF within 5 preferred business days of collection

This document is electronically controlled. Printed copies are considered uncontrolled.

**During the SM Phase only**, the following procedures and assessments will be performed.

- Change-out BioModule as battery limits are reached, return the BioModule to the charging station
- Apply a new fully charged BioModule to the subject and link subject to new BioModule using the Vital Sync™ VPMP
- Clean reusable BioModule and return to the charging station
- Perform daily checks to confirm BioModule and the Vital Sync™ VPMP are communicating and operating properly
- Assess for and document any device deficiencies

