## 11.2. Potential Benefits

Subjects' participation in this study may offer no additional benefit in respect to the same monitoring provided outside of the study.

Possible benefits for participating in this study include the following (although others are possible):

- Subjects in SM arm may benefit from the alternative surveillance monitoring strategy via detection of clinical deterioration during the course of hospital stay.

There is, however, the potential for benefiting future patients should this study lead to the development of safer, more accurate, more cost-effective, and easier-to-use medical monitoring devices.

Since this is not a treatment study, the alternative is to not participate in the study.

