**Confidential**

Protocol #: COVMOPO0561

Rev E 09AUG2017

- Any adverse events noting mild or moderate physiological deterioration
- Any adverse event whose relationship to the study device is: possible, probable, definite, or unknown/ impossible to determine, regardless of what the event may be.
- All SAEs, of any relationship, meeting definition in section 12.2 of the CIP must be reported.

The recording of adverse events for all enrolled subjects begin after the study devices are attached and ends with the subject's completes study enrollment. Completion is defined by when a subject is discharged from the hospital, completes 30 day ( $\pm$  2 days) enrollment period, or if the subject is withdrawn from the study for any reason.

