**Confidential**

## 7.2. General Methodology

In general, descriptive statistics will be used to summarize baseline and study outcomes. For continuous variables, number of available observations, mean, standard deviation, median, minimum and maximum values will be provided. For categorical variables, frequency and percentage will be used. Unless otherwise specified, statistical assessments will be based on 2-sided tests at an alpha level of 0.05, which include Student-t or Wilcoxon rank-sum or ANOVA test for continuous variables, and Chi-square or Fisher's exact test for categorical variables. Multivariate regression models will be used to assess impacts of potential confounding variable. Statistical analysis will be performed using [REDACTED] (SAS Institute Inc., Cary, NC) or other valid statistical software.

The primary effectiveness analysis will be based on all evaluable data from this study. A per protocol analysis will be performed based on all subjects who are compliant with the study protocol, i.e. who provide valid informed consents and do not experience any major protocol deviations.

For safety assessments, adverse events (AEs) will be summarized using frequency counts and percentages. Descriptive statistics will be provided by monitoring group and by severity and relationship. Additionally, differences between the two monitoring groups will be summarized along with 95% confidence intervals. Individual listings of adverse events, including event type, start date, duration, severity, and device-relatedness will be provided as appropriate. The safety analysis will be based on all patients participated in the study.

Further, a health economic analysis will be performed based on healthcare economic and resource utilization data collected in this study. Monitoring effectiveness, QoL in the form of Quality-Adjusted Life-Years (QALYs), life-years gained and other data collected in this study may be used as inputs to the model.

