### 7.10. Safety Evaluation

Only the following adverse events will be collected for this study:

- Any adverse events noting mild or moderate physiological deterioration
- Any adverse event whose relationship to the study device is: possible, probable, definite, or unknown/ impossible to determine, regardless of what the event may be.
- All SAEs, of any relationship, meeting definition in section 12.2 of the CIP must be reported.

The recording of adverse events for all enrolled subjects begin after the study devices are attached and ends with the subject's completes study enrollment. Completion is defined by when a subject is discharged from the hospital, completes 30 day ( $\pm$  2 days) enrollment period, or if the subject is withdrawn from the study for any reason.

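### Between-group adverse event differences include mild or moderate deterioration, which the two groups detect through different monitors, so they mix detection with occurrence

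*SAP*

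**What the plan says.** Protocol 12 and SAP 7.10 limit collection to three classes: "Any adverse events noting mild or moderate physiological deterioration"; events whose relationship to the study device is possible, probable, definite or undeterminable; and all serious events. Neither document gives criteria for the first class or provides for its assessment blind to monitoring.

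SAP 7.2 and Protocol 13.3 summarise adverse events by group, severity and relationship, and add that "differences between the two monitoring groups will be summarized along with 95% confidence intervals". No class is exempted.

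The groups are watched differently. The SM sensor collects "physiologic data including ECG, HR, RR, body orientation, and activity" (Protocol 8.1.2), and the platform is there to "enable clinicians to be notified of clinical distress via color coded alarms and audible alerts" (Protocol 8.4). TM subjects "will be monitored via the site's standard of care telemetry practice/protocol" (Protocol 10.1). Protocol 11.2 says that the SM arm may benefit "via detection of clinical deterioration during the course of hospital stay". In both phases staff are to "Check and record daily AEs/SAEs and protocol deviations" (Protocol 10.2.2). There is no blinding or randomization (Protocol 10.5, 10.6).

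**The concern.** A mild deterioration becomes a recorded adverse event only if someone notices it. The monitor helps to determine that, and the monitor is what differs between the groups. If SM does what Protocol 11.2 hopes, it brings more mild deteriorations to the investigator's attention, and some will be recorded as adverse events under SM. The same success could then read as a safety signal against SM, or could hide a real reduction in deterioration. If telemetry notices more, the distortion runs the other way.

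A 95% confidence interval covers sampling error only. It does not widen for unequal detection, and a larger sample makes it narrower around the wrong value. At stake is how the safety comparison is read, in a study that proposes SM as an alternative to telemetry.

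**Working it through.** **The plan's own figures.** Neither document states an event rate, detection probability or sample size for adverse events. The only sample-size figure is for length of stay. With a coefficient of variation of 0.65, σ = √ln(1 + 0.65²) = 0.5936. The margin is ln 1.2 = 0.1823. At one-sided α = 0.05 and 80% power, n = 2 × (1.645 + 0.842)² × 0.5936² / 0.1823² ≈ 131.1, or 132 per group, as stated. This point does not rest on that figure; it only supplies a group size. The SAP plans 140 per group. The protocol recruits up to 220 and assumes at least 30% attrition, which leaves at most 220 × 0.70 = 154.

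**Model.** Let p be the true proportion of subjects with a mild or moderate deterioration, equal in both groups, and let d be the probability that it is noticed and recorded. The recorded proportion is p × d, so the expected difference (SM minus TM) is p × (d_SM − d_TM). It is zero only if detection is equal.

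**Assumed values.** p = 10-30%, d_TM = 50%, d_SM = 60-90%. The last two columns give the chance that a Wald 95% interval lies wholly above zero, by exact binomial enumeration. With equal detection that chance is about 2.5%.

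| p | d_SM | TM recorded | SM recorded | Spurious difference (points) | n = 132 | n = 220 |
|---|---|---|---|---|---|---|
| 10% | 60% | 5% | 6% | +1 | 5.6% | 6.7% |
| 10% | 90% | 5% | 9% | +4 | 25.8% | 38.3% |
| 20% | 75% | 10% | 15% | +5 | 23.6% | 35.6% |
| 20% | 90% | 10% | 18% | +8 | 47.9% | 68.5% |
| 30% | 60% | 15% | 18% | +3 | 10.1% | 13.4% |
| 30% | 90% | 15% | 27% | +12 | 67.9% | 87.9% |

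For the third row at n = 132, the standard error is √[(0.10 × 0.90 + 0.15 × 0.85)/132] = 0.0406, so the expected interval is 5 ± 8.0 points, or −3.0 to +13.0. At n = 154 the chance for that row is 26.8%.

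**Reverse case.** With d_TM = 75% and d_SM = 50%, the difference is p × (−0.25): −2.5, −5 and −7.5 points for p = 10%, 20% and 30%.

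**Masking.** Suppose SM truly cuts deterioration by a third, from 20% to 13.3%, with detection of 50% under TM and 75% under SM. The recorded proportions are 0.20 × 0.50 = 10% and 0.133 × 0.75 = 10%. The observed difference is zero.

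**What in the plan could separate detection from occurrence?**
- Daily checks in both phases make the review alike, but not the information that reaches it.
- Severity and relationship breakdowns do not show how an event was found. A deterioration that SM revealed but did not cause is still collected and counted.
- The form items in Protocol 12.3 include a description and the date the investigator first noticed the event, but no source of detection.
- Protocol 10.2 confines the tracing of SM alarm times to subjects with a rapid response team intervention or code blue, so milder events have no planned tracing.

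**The case against.** The strongest reply is that the consequence is limited. The interval is a descriptive summary in a pilot study, with no adverse event hypothesis, margin or decision rule. Code blue, unplanned intubation, unplanned ICU transfer and rapid response interventions are already separate secondary endpoints, and individual events are listed. All of this stands. It makes the point one of interpretation, but leaves the pooled difference no easier to read.

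Several stronger readings are tempting and are not supported:

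- *Every SM alarm adds an adverse event.* Protocol 12.2 requires an untoward medical occurrence, and Protocol 12.3 leaves the diagnosis term and severity to the investigator. A threshold crossing is not itself an event.
- *SM misses rhythm changes that telemetry shows.* Protocol 8.1.2 says that ECG is collected continuously, and its sentence on recording is partly redacted. What the site's telemetry shows besides ECG is not described, so a respiratory gap on the TM side is also an inference. The point needs only that the two channels differ.
- *The bias runs against SM.* The documents do not settle the direction.
- *The interval will exclude zero.* Take 30% true deterioration with detection of 50% and 80%, giving 15% against 24%. The interval is +1.6 to +16.4 points at 220 per group. But 220 is a recruitment ceiling that includes screen failures and withdrawals. At the SAP's 140 it is 9 ± 9.2, about −0.2 to +18.2, which includes zero.

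**Conclusion.** The concern holds as a matter of structure. Deterioration events enter the between-group difference, the groups detect them through different channels, and nothing planned separates detection from occurrence. For this class the difference does not estimate a safety effect alone.

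The size is conditional. Under the assumed rates it is +1 to +12 points with no true difference, and −2.5 to −7.5 if telemetry is the better detector. Every rate and detection probability here is an assumption, and no corrected figure can be computed from the documents. A reader might infer that the safety analysis as a whole is invalid, or that the main result is in doubt. Neither follows: the primary length-of-stay analysis is unaffected, and skin reactions and other device effects do not depend on alarm detection. The change is worth making because it is cheap and the interval could otherwise be misread in either direction.

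**What to change.** In SAP 7.2 and 7.10, with Protocol 13.3 aligned:

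1. Keep between-group differences and 95% intervals for serious adverse events and for device-related adverse events, including skin events. Note that serious events are less dependent on the monitor but not independent of it, since prolonged stay and preventive intervention can follow an alarm.
2. Take non-serious deterioration events not related to the device out of the pooled safety difference. Tabulate them by group and by how first detected: telemetry alarm, SM alarm, spot-check or clinical observation. State that any difference reflects detection as well as occurrence.
3. Add one field, 'how first detected', to the adverse event form, and to the item list in Protocol 12.3.

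Do not compare only events first found at spot-checks. Events that SM alarms catch first would leave the SM count and make SM look falsely safer. Protocol 11.3 mentions spot-checks only alongside SM, so an equal schedule under telemetry is not established.

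The cost is a few sentences of SAP text, one extra form field and fewer events in the compared set.

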## 7.3. Center Pooling

N/A – This is a single-center study.

## 7.4. Handling of Missing Data and Dropouts

Sponsor study personnel will review collected data and create data queries for missing data that impacts data analysis. Subjects may withdraw from the study at any time and for any reason. If a subject officially withdraws from the study, the investigator will document the reason and collect final outcomes data from the subject's medical record. No additional follow-up will occur for withdrawn subjects..

## 7.5. Adjustments for Multiple Comparisons

N/A

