Study Procedures and Assessments	
Subjects who meet all of the inclusion criteria and none of the exclusion criteria will be assigned to either one of the monitoring groups and then followed for the duration of their hospital stay.
 
The monitoring groups will be enrolled in two prospective phases: telemetry monitoring (TM) OR surveillance monitoring. Enrollment of the TM group will occur first. After TM enrollment is complete, the enrollment phase of SM will initiate.
 
The TM group will serve as the control group and will be monitored via the site's standard of care telemetry practice/protocol. Subjects will continue to be enrolled in the study if subjects are transferred to medical-surgical unit after initial period of TM. No additional monitoring will be used for duration of study enrollment.
 
The SM group will undergo placement of the study device following study enrollment and hospital staff will implement the SM strategy for the duration of study enrollment. A dedicated medical-surgical unit(s) will be utilized for the SM phase.
 
Study procedures during the hospital stay will involve assessing eligibility, collecting baseline information, documenting clinical data from the eMR, unit transfers, discharges, and evaluating changes in health status.
 
All study related subject data will be documented and entered into the subjects' eCRF. All treatment will be standard of care per institutional practice.

Safety Assessments	Subjects will be monitored for Serious Adverse Events and Device-Related Adverse Events as noted in Section 12.
Statistics	Baseline and study outcomes will be summarized using descriptive statistics. One-way analysis of variance will be used to compare continuous variables (e.g., age, length of study) and Chi-square or Fisher's exact test will be used for categorical variables. Multivariate regression will be used to assess impacts of potential confounders. A P-value <0.05 is considered statistically significant unless otherwise specified.

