**13.2. Hypotheses and Endpoints**

The primary study endpoint is hospital of length of study (LOS), which is calculated from date of admission and discharge. The primary objective is to demonstrate that LOS of the SM group is similar (non-inferior) to the TM group.

[Redacted]

This document is electronically controlled. Printed copies are considered uncontrolled.

Additionally, if the non-inferiority objective is met, superiority will also be assessed (without statistical penalty) to further understand the effectiveness of SM versus TM. The corresponding superiority hypothesis [REDACTED] e., SM has shorter LOS duration than TM).

Secondary clinical and qualitative endpoints include:

- number of RRT interventions between monitoring groups
- survival rates post RRT interventions between monitoring groups
- Time of RRT activation to time of threshold notifications from SM system following clinical deterioration events
- code blue rates between monitoring groups
- unplanned intubations between monitoring groups
- clinical team satisfaction with surveillance monitoring and study product
- patient satisfaction with surveillance monitoring and study product
- perceptions of clinicians who prescribe telemetry to patients without AHA indication
- Clinicians' perceptions on telemetry utilization and impact on hospital resource utilization and patient flow

Additionally, healthcare economic and resource utilization data will be collected to evaluate:

- telemetry bed, ED, and ICU bed availability between monitoring periods
- associated health care costs between monitoring periods
- the number of ICU, ED, PACU, and telemetry delays in transfer between monitoring periods
- the number of hospital unit transfers between monitoring groups
- the number of unplanned ICU transfers between monitoring groups
- ICU LOS for subjects who have an unplanned transfer to the ICU between monitoring groups
- the number of unnecessary diagnostic tests and therapeutic procedures generated by artifacts and/or misdiagnosis between monitoring groups

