##### 4.1.2. Secondary Healthcare Economic and Resource Utilization Objectives

1. Compare telemetry bed, emergency department (ED) bed, and intensive care unit (ICU) bed availability between monitoring periods
2. Compare associated health care costs between monitoring periods
3. Compare the number of ICU, ED, PACU, and telemetry delays in transfer between monitoring periods
4. Compare the number of hospital unit transfers between monitoring groups
5. Compare the number of unplanned ICU transfers between monitoring groups
6. Compare ICU LOS for subjects having unplanned transfers to the ICU between monitoring groups
7. Compare the number of unnecessary diagnostic tests and therapeutic procedures generated by artifacts and/or misdiagnosis between monitoring groups

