##### 4.1.3. Secondary Clinical and Qualitative Objectives

1. Compare the number of Rapid Response Team (RRT) interventions between monitoring groups
2. Compare survival rates post RRT interventions between monitoring groups
3. Compare code blue rates between monitoring groups

This document is electronically controlled. Printed copies are considered uncontrolled.

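### Secondary comparisons default to unadjusted two-sided 0.05 tests that may be called statistically significant, with multiplicity set to N/A and no order, gate or exploratory label

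*SAP*

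**What the plan says.** **Multiplicity.** Under the SAP 7.5 heading "Adjustments for Multiple Comparisons" the entire entry is N/A.

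**Significance rule.** The Statistics row of the Protocol synopsis (section 4) states "A P-value <0.05 is considered statistically significant unless otherwise specified". SAP 7.2 adds "Unless otherwise specified, statistical assessments will be based on 2-sided tests at an alpha level of 0.05". Protocol 13.3 and SAP 7.7 repeat that default. No section specifies anything different for the secondary endpoints.

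**Primary endpoint.** Protocol 13.2 and SAP 7.9 describe one ordered procedure: LOS non-inferiority first and, only if that is met, LOS superiority at no alpha cost.

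**Secondary endpoints.** SAP 4.1.2 lists seven economic and resource objectives, all worded as comparisons. Two are composite: "Compare telemetry bed, emergency department (ED) bed, and intensive care unit (ICU) bed availability between monitoring periods" and "Compare the number of ICU, ED, PACU, and telemetry delays in transfer between monitoring periods". SAP 4.1.3 lists nine clinical and qualitative objectives. Four compare monitoring groups, for example "Compare code blue rates between monitoring groups". One concerns the timing of alerts from the SM system alone, and four survey objectives are worded as assessments. SAP 7.9 lists the secondary endpoints again without assigning a test to any of them.

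**The concern.** SAP 7.5 is where a reader would look for the status of the secondary p-values, and it gives none. With the synopsis rule in force, any secondary P<0.05 can be reported as statistically significant, whatever LOS shows and however many comparisons were made.

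The stated purpose of the study covers clinical, economic, resource and qualitative outcomes, and Protocol 15.9 says publication is planned. As written, the plan would allow LOS to miss non-inferiority while a chance gain in bed availability, transfer delays or cost is called significant. A chance difference against SM could be over-read in the same way.

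**Working it through.** **Is there a figure to reproduce?** The documents give no family-wise error rate for the secondary endpoints. The only sized hypothesis is LOS: 132 per group, coefficient of variation 0.65, margin 0.2 on the mean ratio (Protocol 13.1, SAP 6). On the log scale, SD = √ln(1 + 0.65²) = 0.5936 and margin = ln 1.2 = 0.1823. At one-sided 0.05 and 80% power, n = 2 × 0.5936² × (1.645 + 0.842)² / 0.1823² ≈ 131.1, rounded up to 132. This reproduces the stated number and shows that the sample size addresses LOS alone.

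**Counting the family from the objectives' wording.**
- By objective: 7 (SAP 4.1.2) + 4 (SAP 4.1.3: rapid response team (RRT) interventions, survival after RRT, code blue, unplanned intubation) = 11.
- By component: beds 3, cost 1, delays 4, unit transfers 1, unplanned ICU transfers 1, ICU LOS 1, unnecessary tests 1 = 12; plus the 4 clinical = 16.
- Non-event objectives only: beds, cost, delays, unit transfers = 4. The other seven count clinical events or arise only after one.

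**Independent tests, no true effect.** P(at least one P<0.05) = 1 − 0.95^k.
- k = 4: 18.5%
- k = 11: 43.1%, with 11 × 0.05 = 0.55 false positives expected
- k = 16: 56.0%, with 16 × 0.05 = 0.80 expected
- The probability first passes one half at k = 14 (51.2%).

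**Correlated tests.** Assume equicorrelated normal statistics Zᵢ = √ρ·U + √(1−ρ)·eᵢ and find P(max|Zᵢ| > 1.96). The documents give no correlations, so ρ is varied.

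| k | ρ = 0 | ρ = 0.3 | ρ = 0.5 | ρ = 0.8 |
|---|---|---|---|---|
| 4 | 18.5% | 17.4% | 15.6% | 11.4% |
| 11 | 43.1% | 37.5% | 30.4% | 18.0% |
| 16 | 56.0% | 47.6% | 37.4% | 20.7% |

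**Rare events.** Fisher's exact test runs below its nominal level. At 132 per group, its true size at nominal 0.05 is 0.0012, 0.0091, 0.0224 and 0.0304 for assumed event rates of 1%, 2%, 5% and 10%. Five of the 11 objectives are treated as rare: code blue, intubation, RRT, unplanned ICU transfer and survival after RRT. The other six stay at 0.05, and tests are taken as independent.
- Lower rates (1% for code blue and intubation, 5% for RRT and ICU transfer, size 0 for survival after RRT): 1 − 0.95⁶ × 0.9988² × 0.9776² = 29.9%.
- Higher rates (2%, 10%, size 0.01): 1 − 0.95⁶ × 0.9909² × 0.9696² × 0.99 = 32.8%.
- For 16 components (0.95¹¹ in place of 0.95⁶): 45.8% and 48.0%.

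**The case against.** Several points against this stand.

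- **No stated rate is breached.** The 0.05 in the synopsis and SAP 7.2 applies to each test. Setting a family-wise probability against it shows no broken promise, because none was made for the secondary endpoints.
- **Testing is a default, not an assignment.** SAP 7.2 opens by saying outcomes are generally summarised descriptively, and SAP 7.9 assigns no endpoint-specific test. A reader might infer that every secondary endpoint will be tested; the documents do not go that far. But the same SAP 7.2 paragraph continues with hypothesis tests, and 11 objectives are worded as comparisons.
- **A false positive is not shown to be more likely than not.** A reader might infer that it is. With 11 tests the figure stays below one half even under independence, and 16 tests exceed it only when nearly independent and at full size. Bed and delay measures from one hospital over the same two periods are unlikely to be independent.
- **The surveys should not enlarge the count.** The clinician questionnaires have PRE and POST forms, so a reader might add two more tests. Their objectives are worded as assessments and no PRE/POST test is stated.
- **It is a single-center pilot resting on one primary endpoint.** This limits the importance of the point. Yet the pilot label is attached to no endpoint and does not qualify the synopsis rule, and the study carries a powered non-inferiority hypothesis.

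What the objection does not remove is the combination of N/A, an unqualified significance rule and the absence of any exploratory label.

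**Conclusion.** The point holds as a gap in what the plan allows to be claimed, not as an error in the primary analysis. The LOS sequence is fixed in order and needs no adjustment.

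The size depends on how many of the comparisons are tested and how correlated they are. The widest range is 11.4% (4 tests, ρ = 0.8) to 56.0% (16 independent tests). At ρ = 0.5 the figure is 30.4% for 11 tests and 37.4% for 16. Correlations and event rates are assumptions.

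All these figures also presume tests that are valid under the null. SM follows telemetry in time without randomization, so calendar differences could produce P<0.05 with no SM effect. A reader might infer that a formal correction such as Holm would then support confirmed resource benefits. It would not, because multiplicity adjustment does nothing about period confounding. Clear labelling is the proportionate remedy.

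**What to change.** 1. **SAP 7.5.** Replace N/A with a statement that LOS (non-inferiority, then superiority, in fixed sequence) is the only confirmatory family. State that all endpoints in 4.2.2 and 4.2.3 are exploratory, reported with estimates, 95% confidence intervals and nominal unadjusted p-values, and not declared statistically significant. State that this includes the patient-safety endpoints, left unadjusted so that signals of harm are not suppressed.
2. **Protocol synopsis, Statistics.** Limit the P<0.05 sentence to the LOS sequence.
3. **Protocol 13.3, SAP 7.2 and SAP 7.7.** Add a cross-reference to SAP 7.5 beside the default 0.05 wording, so the general rule does not override it.

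No adjusted testing route for the secondary endpoints is proposed.

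The cost is a few sentences in the SAP, one in the synopsis and the cross-references. No data, patients or primary analyses change. The real downside is that the sponsor gives up significance wording for secondary results.
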